- (4) MRI: The nature of the scanner environment will be explained to all participants during the consent process (i.e., you will lay on a table that slides into a narrow cylinder, you will be asked to lie still, the machine makes very loud noises, you will be provided ear protection). Participants will be informed that they may stop the study at any time by informing study staff via intercom or squeezing a safety bulb placed near or in their hand. To minimize the risk of claustrophobic reactions, participants will be screened for claustrophobia. Additionally, participants will be informed that if any heating they experience becomes uncomfortable, they should inform study staff and they may discontinue participation at any time without penalty. To reduce the possible physical risks associated with MRI, participants will be thoroughly screened by study personnel and the Brown MRI Research Facility staff prior to entering the magnetic field for the presence of any metallic objects, implants, or other safety risks, and they will have all possible risks explained to them verbally and in writing using a separate consent form at the Brown Facility. If MRI scans lead to the discovery of a previously unknown potential health problem, study staff will notify these participants as soon as possible, and appropriate recommendations will be made for further investigation by qualified medical personnel. Although the scan is not diagnostic in nature, and the study personnel and MRI technician are not qualified to make diagnoses based on imagery data, any findings warranting possible further attention will be shared with the participant and the participant will be instructed to follow-up with qualified medical personnel.
- (5) CES: To minimize risks due to CES, all participants will be carefully screened for contraindications to CES as listed in the exclusion criteria. As the risks of CES during pregnancy are unknown (although most likely not harmful), pregnant individuals are excluded from participation based on historical guidelines. Use of an electrically isolated power source (i.e., battery-powered stimulation device) also protects against delivery of more intense currents than intended. Stimulation parameters (current and frequency) will be preset and tested for tolerability during Visit 1 under the guidance of Drs. [REDACTED] [REDACTED]. Participants will be told that modification of the Alpha-Stim device or accessories is not allowed, and that doing so could result in injury. They will also be told to not stimulate directly on the eyes or press the probes over the carotid sinus (on the neck near the larynx) and application of the electrodes near the thorax may increase the risk of cardiac fibrillation, as well as that it is advised to not use dangerous machinery or vehicles during treatment days, and that for that reason CES should only be applied/used on off-duty days or after completion of a duty cycle. Participants will have the option of discontinuing the study at any time and will be explicitly instructed to contact the research team if they experience any discomfort. The research team will reach out to participants at least once per week during the four weeks of CES (or more often if indicated based on incomplete EMA surveys or difficulties using the CES device). To assess for presence of adverse events, we will use a recently adapted Side Effects Questionnaire based on the one developed by Brunoni and colleagues [26]. If there is any doubt about the mental or physical status of an individual during the CES intervention, participants will be evaluated by Dr. [REDACTED] in her role as clinical psychologist, who will make recommendations for follow-up care, if required. Telephone or in-person follow-up will be arranged as needed and will not be considered a protocol deviation. Any participant judged on clinical grounds to have suffered adverse effects will thus be evaluated and treated as necessary and withdrawn from the study if deemed necessary.
- (6) EMA: Participants will be told that EMA survey reminders can be silenced to avoid interference with work-related duties, and that two reminder notifications will be sent to participants to allow completion of surveys at a later time when convenient before they expire.
- (7) Oura ring: Participants will be told that if they experience skin irritation to stop wearing the Oura ring and contact the study team. Participants will also be told to be cautious that the ring does not get caught on fixed structures or heavy objects or when working with other objects that contain batteries

as this could cause a potentially dangerous electric shock.

(8) Inconvenience and burden of required time/travel: Remuneration will be offered to cover part of the subject's expenses related to participation in this research study, but subjects will not be offered reimbursement for all the expenses they may incur (e.g., gas). Butler Hospital is about a ~10-minute drive away from the Brown University MRI Research Facility, and Butler Hospital and the Brown MRI Research Facility have (dedicated, free) parking spots for participants undergoing study-related procedures/MRIs. Our experience has been that research participants generally have no difficulty accessing either location.

(9) Other: The research staff will evaluate participants prior to and post CES as well as regularly monitor participants for side-effects/adverse events during the four-weeks of CES. Dr. [REDACTED] is a clinical psychologist at Butler Hospital with training in and experience with neuromodulation and available to evaluate that participation continues to be safe and reasonable for participants.

Please note: **Emergencies:** If, during any study procedure, staff identifies a condition that mandates immediate clinical intervention or official reporting, all necessary steps will be taken including following local (Butler Hospital) emergency procedures.

D2. Measures to Ensure Confidentiality

Every effort to maintain participant confidentiality will be made. All research personnel will be trained in the responsible conduct of research. All study forms and data will be identified only by a unique participant ID number, and will be stored in locked file cabinets or on secure research servers or CNE REDCap. Identifying information (contact information, name, consent documents) will be separated from the research data and be stored separately in a different locked file cabinet. All computerized/digital data will be stored on a secure research server at Butler Hospital and/or University of Rhode Island, separated from identifiers. REDCap data that includes identifiers will be saved in a database separate from a database that includes only coded data. Hard copies of data capture forms, e.g., descriptive data and MRI/CES safety screening, will be kept in locked file cabinets in the Annex 3rd Floor Research Lab space at Butler Hospital. EMA data collected through LifeData is HIPAA-compliant. Data collected from the Oura ring is being securely processed through anonymization or pseudonymization of personal data, strict access control, and the use of encryption to protect the data. Oura's data privacy practices are maintained in compliance with the California Consumer Privacy Act of 2018 (CCPA) and the General Data Protection Regulation (GDPR). All data will be permanently deleted from the Oura Cloud after all data collection, data back-ups, and data analyses are completed – This only pertains to data saved with the Oura Cloud. We will retain any data obtained through the Oura ring locally at Butler Hospital. Only authorized study personnel will have access to the data. No personal participant information will be presented in any publication or presentations resulting from this research. Please note: the CES device does not generate any data. Research data will be destroyed 6 years after research study activities have been concluded.

D3. Data Safety Monitoring Plan

To meet the NIH policy for Data and Safety Monitoring, we have created a system for oversight of the project. Oversight and internal monitoring of the participants' safety will be conducted by the investigator team, given the unique expertise of each investigator. Both Drs. [REDACTED]

[REDACTED] have extensive experience conducting non-invasive neuromodulation in individuals presenting with a variety of (sub)clinical psychiatric symptoms, including anxiety, posttraumatic stress, and depression. Specifically, Drs. [REDACTED] have ongoing projects utilizing electrical current stimulation supported by the COBRE Center for Neuromodulation project and which are performed at Butler's Neuromodulation Research Facility. Dr. [REDACTED], as a clinical psychologist and Director of the Study of Trauma, Risk-taking, Emotions, and Stress Symptoms (STRESS) Lab, has substantial background in the pathogenesis of posttraumatic stress disorder. Likewise, [REDACTED] projects mainly involve the use of non-invasive brain stimulation techniques in individuals with posttraumatic stress disorder. All participants will be carefully screened prior to study entry, and the application of and device settings for CES will be

practiced and set prior to providing the CES device to participants. Other participant safeguards with respect to study procedures are described in Protection of Human Subjects. A member of the research team will be available during working hours, and the research team will check-in with participants at least once a week. In the event of any adverse event, Dr. [REDACTED] as study PI will be contacted to facilitate subsequent assessment and treatment or referral as necessary.

In the event of any participant becoming unstable or demonstrating worsening of clinical symptoms during the study duration, study procedures will be stopped for this individual and Dr. [REDACTED] as study PI will be contacted and she will follow-up with Drs. [REDACTED] in their role as clinical psychologist as well as the on-call physician at the Butler Hospital TMS Clinic. In case, Dr. [REDACTED] is not available, the on-call physician at the Butler Hospital TMS Clinic will be contacted to facilitate treatment or referral. In case of emergency medical assistance, the study team will contact 911 and/or the Brown University EMS response team depending on severity and location (e.g., while at the Brown University MRI Research Facility). All research staff as well as MRI facility staff members at the Brown University MRI Research Facility are trained in basic first aid, CPR, and MRI safety and evacuation protocols.

To ensure the integrity of the data all data will be reviewed for errors or inaccuracy within one week after it is obtained. All data will be entered into a research database (i.e., CNE REDCap) as it is collected, and research staff will meet with the supervising co-Project Leader at least weekly or as appropriate to review ongoing subject data. Additionally, Drs. [REDACTED] will meet at least weekly to discuss the project, at which time they will review progress about enrollment, any adverse events, and attrition/noncompliance, review data quality, recruitment, and study retention, and examine other factors that may affect outcome. Circumstances surrounding any identified adverse events, incidents of subject dissatisfaction, or subject noncompliance or withdrawal of consent will be tracked regularly and discussed to determine any changes in participant risk.

The co-Project Leaders [REDACTED] will hold primary responsibility for monitoring study safety and progress. Per IRB requirements, they will be responsible for assessing, tracking, and reporting, as necessary, any adverse events or unanticipated effects during the study to the IRB of Record (Butler Hospital). Following standard practice, serious and unexpected adverse events will be reported to the IRB of Record within the designated guidelines. For example, a serious adverse event will be reported via IRBNet within the IRB guidelines. The written report will indicate whether the serious adverse event was attributed to the study. The project Standard Operation Procedure binder will provide detailed operating procedures including the definitions of SAEs and AEs and reporting requirements. If a pattern or potential pattern of unexpected adverse events emerges during the study, Drs. [REDACTED] will discuss this pattern with outside physicians with expertise in brain stimulation in this population. The PI of the COBRE Center for Neuromodulation ([REDACTED]) will in turn be responsible for reporting safety events to the NIH.

D4. Data Management and Sharing Plan (DMSP)

N/A; proposed research is an administrative supplement to a grant (NIMHS COBRE CCN at Butler Hospital) approved for funding prior to January 25, 2023.

E. Potential Benefits

None of the assessment and experimental methods are to be diagnostic in nature or intended to treat any (mental) health condition and therefore will not be of any direct benefit to participants. However, the knowledge gained may be of potential benefit to society by starting to gain insight into whether, and how, CES might be developed as a preventative intervention for PTSD. Additionally, given that the Alpha-Stim AID CES is FDA cleared for anxiety and/or insomnia, participants who experience anxiety and/or insomnia might see a change in these symptoms.

F. Risk-Benefit Ratio

The results of this study will provide important data on whether a four-week course of CES (and related study procedures) is feasible and acceptable in active-duty firefighters. Additionally, we hope to obtain preliminary signal of changes due to cranial electrotherapy stimulation on subjective (e.g., anxiety, sleep, mood) and/or objective (e.g., neural) variables related to homeostasis. Knowing which measures might be sensitive to detect changes due to cranial electrotherapy stimulation will directly inform the design of a future, collaborative clinical trial to test efficacy of CES for the prevention of PTSD in first responders. Given the high likelihood for the development of PTSD in first responder firefighters, the benefits to knowledge to be collected with this study outweigh the risks.

4) REFERENCES

1. Smith, S.M., R.B. Goldstein, and B.F. Grant, *The association between post-traumatic stress disorder and lifetime DSM-5 psychiatric disorders among veterans: Data from the National Epidemiologic Survey on Alcohol and Related Conditions-III (NESARC-III)*. Journal of psychiatric research, 2016. **82**: p. 16-22.
2. Shalev, A.Y., et al., *Prospective study of posttraumatic stress disorder and depression following trauma*. American Journal of psychiatry, 1998. **155**(5): p. 630-637.
3. Thomas, J.L., et al., *Prevalence of mental health problems and functional impairment among active component and National Guard soldiers 3 and 12 months following combat in Iraq*. Archives of general psychiatry, 2010. **67**(6): p. 614-623.
4. Galovski, T. and J.A. Lyons, *Psychological sequelae of combat violence: A review of the impact of PTSD on the veteran's family and possible interventions*. Aggression and violent behavior, 2004. **9**(5): p. 477-501.

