COVER PAGE – STUDY PROTOCOL

Title: Cranial electrotherapy stimulation: Piloting a road to PTSD prevention in first responders

NCT number: NCT06203717

Document date: 08/15/2024

BUTLER HOSPITAL
INSTITUTIONAL REVIEW BOARD
PROTOCOL

Project**Title of Project:** Cranial electrotherapy stimulation: Piloting a road to PTSD prevention in first responders**Short Title of Project:** CES in firefighters**Principal Investigator (PI):** [REDACTED]**Other Investigator(s):** [REDACTED]**Revision History:**

Version Number	Version Date	Summary of Revisions
1.0	08/28/2023	First version submitted
	09/18/2023	First version approved
2.0	12/14/2023	
 1. Changed PI from [REDACTED]. 2. Added [REDACTED] as co-investigator to the study team. 3. Corrected error in ecological momentary assessment (EMA). 4. Added new advertisement material.
3.0	05/28/2024	
 1. Revised CNE Research Application to change Device Risk Level to "nonsignificant risk device" instead of "N/A". 2. Updated protocol to include XNAT – a password protected secure server – for transfer of MRI data from MRF to Butler. 3. Broadening of recruitment locations to include community locations (e.g. coffee shops).
4.0	8/15/24	
 1. Broadening of recruitment methods through social media marketing. 2. Update protocol to allow for texting for initial outreach to potential participants.

Description of Study**A. Specific Aims**

Aim 1: Test the feasibility and acceptability of Cranial electrotherapy stimulation (CES) in firefighter first responders.

Prediction: CES is feasible quantified as more than 75% of sessions completed, and acceptable quantified as less than 20% attrition in the sample, such that at least 16 out of 20 firefighters complete, for example, at least 15 out of 20 sessions over the course of four weeks.

Aim 2: Test the effects of CES on subjective homeostatic functioning in firefighter first responders.

Prediction: CES will reduce subjective fatigue and frequency and intensity of negative emotions (e.g., distressed, nervous) while increasing the experience of positive emotions (e.g., calm, inspired) assessed naturalistically in near real-time through ecological momentary assessments (EMA).

Aim 3: Test the effect of CES on objective homeostatic functioning in firefighter first responders.

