Critical Gaps in Knowledge. Despite CES' potential for use in first responders, there are no studies that evaluate if a predefined four-week course of CES is feasible and acceptable in firefighters. Although one study examined CES in a sample of 86 first responders consisting mainly of law enforcement as well as 10 firefighters, participants were "permitted to use the device any time of day and for any indication" [c.f. 17] and the report does not mention of how often, at what time of day, and for how long participants used the device or whether

there were difficulties with its use, providing no information about feasibility or acceptability. This is important because it is advised to avoid the use of heavy machinery after CES. Therefore, the application of CES should be carefully integrated with the firefighter work schedules, starting with its use only on off-duty days.

Additionally, there are no studies that test the effects of CES on subjective and objective indices of homeostatic functioning in active-duty firefighters to gain insight into possible mechanisms of CES-modulatory effects. In fact, despite a literature on effectiveness for anxiety, insomnia, and depression [but see 18 for a negative randomized controlled trial], the mechanism of CES effects on homeostatic functioning remains rather hypothetical with little direct evidence [19].

Here we propose to address these critical gaps in science by testing if a course of four weeks of CES in firefighters is 1) feasible and acceptable in this population; 2) impacts subjective variables associated with homeostasis, including fatigue, frequency and intensity of negative and positive emotions (i.e., distressed, nervous, calm, inspired); and 3) changes objective variables associated with homeostasis, including functional and structural neural connectivity, heart rate variability, and sleep quality in a subset of participants.

C. Experimental Method

C1. Brief Description of Subjects

Participants will be 20 active-duty firefighters in the State of Rhode Island, between 18-56 years old.

Participants will be of any racial or ethnic group and of any gender.

C2. Study Design

This study will use a within-subject design, with all participants completing all experimental procedures with no difference to how CES will be applied. Recruitment of 20 participants incorporates an estimated 20% attrition to allow data collection on 16 participants.

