ensure participants understand all procedures as well as assess tolerability of the individually determined stimulation intensity prior to sending participants home with the Alpha-Stim AID CES device. The device manual, a quick set-up guide for ease of reference, as well as information on the determined intensity and a pen-and-paper tracking log will be provided to participants to be used during the four-weeks of at home administered CES. Throughout the four weeks of CES, participants will be asked to document the day, time, and duration of CES application using the provided tracking log. Participants will be instructed to only use the Alpha-Stim AID CES device on 'off-duty days' (i.e., days on which they are not working). This is done as an extra precaution to avoid potential negative effects of CES on work-related performance as using heavy machinery immediately following CES is not advised per device manufacturer. The research team will check in with the participant at least once per week (or more often if indicated based on incomplete EMA surveys or difficulties using the CES device), during the four weeks of CES, starting on the second day after starting CES. This check-in will allow obtaining feedback on user feasibility as well as allow assessment for the presence of side effects/adverse events. We will use a recently adapted Side Effects Questionnaire based on the one developed by Brunoni and colleagues [26]. Participants will also be provided with a contact phone number in case they experience side effects/adverse events prior to study staff check-ins or in case questions or other issues arise. Participants will be reminded that if they experience vertigo (a dizzy feeling, similar to the sensation of rocking on a boat) despite the predetermined intensity set during the in-person visit at Butler Hospital, they should decrease the intensity immediately until the dizziness stops.

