The Project Leaders of this supplement, [REDACTED] will be responsible for and supervise data collection and data management. The main goals of this study involve assessing feasibility (i.e., > 75% of CES sessions completed) and acceptability (i.e., < 20% attrition in the sample) of a 4-week course of CES in active-duty firefighters (i.e., at least 16 out of 20 firefighters complete at least 15 out of 20 sessions over four weeks) and obtaining preliminary signal of effect to inform the design of a future, collaborative clinical trial to test efficacy of CES for the prevention of PTSD in first responders. Our primary outcome measures include the number of completed sessions to quantify feasibility and attrition in the sample assessing acceptability (Aim 1). In addition, we will collect data on subjective fatigue, negative and positive emotions using ecological momentary assessment (Aim 2) as well as heart rate variability and sleep quality (Aim 3). Finally, we will collect pre- and post-CES data on clinical symptoms (PTSD, depression, anxiety) and MRI-based resting state functional connectivity and structural connectivity (Aim 3). Given the preliminary nature, the proposed study is not designed to have adequate power to robustly test whether CES is effective for PTSD prevention, which would constitute the long-term goal of the proposed work. As such the proposed number of 20 individuals is solely meant to achieve the listed aims.

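### The two statements of which days CES may be used need reconciling, and no daily duty record is described that would explain a shortfall against 15 of 20 sessions

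*Combined protocol and SAP*

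**What the plan says.** **The day rule.** The CES paragraphs of section C3 limit use to off-duty days ("i.e., days on which they are not working"), as an added precaution about work performance. Section D1, item (5), also describes what participants are told. The rule there is "CES should only be applied/used on off-duty days or after completion of a duty cycle", and the words leading into it give its ground: "it is advised to not use dangerous machinery or vehicles during treatment days, and that for that reason". The phrase about a duty cycle occurs only there and has no definition. Section B (Critical Gaps in Knowledge) speaks of "starting with its use only on off-duty days", which agrees with C3.

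**The target.** Section A (Aim 1) predicts that "at least 16 out of 20 firefighters complete, for example, at least 15 out of 20 sessions" will be done, and section C4 repeats "at least 15 out of 20 sessions over four weeks". C4 names the number of completed sessions as a primary outcome.

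**The records.** Under C3, participants "document the day, time, and duration of CES application using the provided tracking log". Section D2 says that the device produces no data. The daily EMA content described in C3 is affect and fatigue, with weekly questions on stressful events. Staff check in at least weekly: "This check-in will allow obtaining feedback on user feasibility", along with side effects. There is a debriefing at Visit 4, section D3 provides for tracking the circumstances of noncompliance, and up to 10 participants wear an Oura ring on off-duty nights.

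**The concern.** Two linked things are left open.

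First, the *or* in D1 appears to add an occasion that C3 does not list. A firefighter coming off shift in the morning could conclude from D1 that a session later that day is allowed, and from C3 that it is not. The rule exists for safety at work, so participants and staff need a single version of it.

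Second, the number of sessions a firefighter can do depends on the roster, while the target is a fixed 15 of 20. A log of sessions done has no entry for a day without CES, so it does not show whether that day was a duty day. If the target is missed, the designers of the next trial need to know whether firefighters left permitted sessions undone or whether the day rule left too few days, because the remedies differ. Section B itself faults the earlier first-responder study for not reporting how often and when the device was used, and asks that CES be fitted carefully to work schedules.

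**Working it through.** **1. The plan's own figures.** 16 / (1 − 0.20) = 20, so the recruitment figure in C2 reproduces. The session benchmark is 15/20 = 0.75, and 16 completers of 20 means 4/20 = 0.20 attrition.

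**2. The wording side by side.** C3 permits off-duty days only. D1 permits off-duty days, or a time after a duty cycle is complete.
- Broad reading: the day on which a run of shifts ends becomes available once the shift is over. D1 is then wider than C3.
- Narrow reading: the D1 phrase means the off days that follow a run of shifts. The two then coincide, and the difference is 0.

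**3. A bound that needs no roster.** Inputs: 28 days (section D, Material Inducements, counts 28 daily surveys), a maximum of 20 sessions (same section), and the 15-session target. Assumption: one session per day.
- 15 sessions leave at most 28 − 15 = 13 days without permitted CES (13/28 = 46%).
- 20 sessions leave at most 28 − 20 = 8 such days (8/28 = 29%).
- The criterion needs 16 of 20 firefighters, so 20 − 16 + 1 = 5 participants with more than 13 such days would be enough to miss it. This too holds only at one session per day.

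**4. Illustration on assumed rosters.** The documents give none. I took four, counted over 28 days for every possible start day. The 24 h and 48 h duties start at 08:00; the day/night roster has days 08:00–18:00 and nights 18:00–08:00.

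Convention A: C3 excludes any calendar day containing a duty hour, and D1 adds back the day a run of shifts ends (the broad reading).

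Convention B: a shift counts only against the duty day on which it starts (48 h counts as two duty days). The day it ends is then already off duty under both rules.

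| Assumed roster | A: C3 | A: D1 | A: difference | B: both rules | B: difference |
|---|---|---|---|---|---|
| 24 h on / 48 h off | 9–10 | 18–19 | 9–10 | 18–19 | 0 |
| 24 h on / 72 h off | 14 | 21 | 7 | 21 | 0 |
| 48 h on / 96 h off | 13–15 | 18–20 | 4–5 | 18–20 | 0 |
| two days, two nights, four off | 9–12 | 12–16 | 3–4 | 12–16 | 0 |

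Under A, the C3 rule leaves fewer than 15 days in three of the four rosters and reaches 15 for only some start days in the 48/96 roster. The D1 rule gives at least 15 in three rosters, and for only some start days in the fourth. Under B, both rules give what D1 gives under A.

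**5. Why the log cannot explain a shortfall.** Let P be the number of permitted days, at one session per day, for a participant who logs 12 sessions. Sessions not permitted = max(0, 20 − P). Sessions permitted but not done = min(P, 20) − 12.
- P = 12: 8 not permitted, 0 not done.
- P = 16: 4 and 4.
- P = 20 or more: 0 and 8.

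The same log fits all three.

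**The case against.** **The two statements may not conflict.** D1 gives its reason in the same sentence, and that reason concerns whole treatment days, which favours the narrow reading. This stands as far as it goes: a reader might infer two flatly opposed rules, and the text does not establish that. It establishes an undefined term whose broad reading departs from C3. On the narrow reading the *or* clause adds nothing, and nothing tells staff or participants to read it that way.

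**The day counts are invented.** No roster, start time or calendar-day convention comes from the documents, and no section limits sessions to one a day. This also stands. The table shows that a definition is needed; it does not estimate an effect. A reader might infer that the C3 rule puts 15 sessions out of reach for these firefighters, but that result belongs to one convention on assumed schedules.

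**The primary outcome is untouched.** Correct. A reader might infer that a session done on a disputed day would be dropped from the count. No section removes a session because of the day it was done.

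**Reasons for missed sessions already have routes.** The weekly check-ins, the Visit 4 debriefing and the noncompliance tracking could each yield reasons, and a roster could be matched to log dates afterwards. These narrow the gap. None is described as a daily duty record, no section plans to obtain rosters, and a session skipped because the rule forbade it is not noncompliance. Oura wear covers at most 10 of 20 participants, and a night without data need not be a duty night. The log form and full EMA item list are not reproduced in the protocol, so the point is limited to what is described.

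**Conclusion.** The point holds in limited form. C3 and D1 (5) state a safety instruction in two ways, one resting on an undefined term, and they must be reconciled. The possible difference is 0 to 10 permitted days in 28 on the four assumed rosters at one session per day: 0 on the narrow reading or when shifts are counted by starting day, and 3 to 10 on the broad reading when every calendar day touched by a shift is excluded.

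Aim 1 can still be answered, since whether the course was completed follows from the count. What is missing is a described means of explaining a failure. That conclusion depends on neither the rosters nor the choice of rule, only on the absence of a described day-by-day duty record. It does not invalidate the feasibility criterion, but it is worth correcting because the pilot is meant to inform the design of a later trial.

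**What to change.** 1. Reconcile C3 and D1 (5) so that one rule governs, and define duty cycle, including how the day a shift ends is treated. Which rule applies is for the investigators to decide.
2. Add one daily duty-status item to the EMA: on duty, off duty, or came off duty today. This is preferable to collecting employer rosters, which adds employment-linked data to a study that already lists discovery of participation by colleagues as a risk. The alternative is to record the roster at the weekly check-ins.
3. Leave the primary criterion unchanged. Beside it, report sessions completed / sessions permitted, with missed sessions classed as not permitted or permitted but not done, and state the sessions-per-day convention behind the denominator.

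Cost: a protocol revision, a few seconds of survey time per day, and no duty data for participants who have already finished. Duty status will also be missing on days when the survey is missed, though the check-in calls could recover some of it.

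Separately, align the threshold wording in sections A and C4: 15/20 is exactly 75% and 16 completers of 20 is exactly 20% attrition, while the text asks for more than 75% and less than 20%.
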